6.2.2. Open-Label Extension Design

Patients may be evaluated for eligibility in the open-label extension using values from the Week 108 visit as screening assessments. Patients with an eGFR <30 (but >20) mL/min/1.73 m² will be eligible for participation in the open-label extension at the discretion of the Investigator, but will require close monitoring of eGFR and serum potassium (see [Section 7.2.2](#)).

For patients who agree to participate in the open-label extension and meet eligibility criteria (see [Section 7.2](#)), the Week 112 visit will also serve as the baseline visit for the open-label extension. Standard-of-care treatment (ACEI and/or ARB therapy) will be discontinued before the Week 112 visit. The final dose of an ACEI and/or ARB should be taken on the day before the Week 112 visit. At this visit, patients will sign a new informed consent (if not completed previously) for the open-label extension and begin taking open-label sparsentan. All Week 112 evaluations must be completed prior to the first dose of open-label sparsentan.

[figure not shown]
Patients who are taking 2 or 4 capsules of study medication (ie, 400 mg or 800 mg sparsentan or 150 mg or 300 mg irbesartan) at the end of the double-blind period will initiate treatment in the open-label extension at one-half the corresponding dose of open-label sparsentan for the first 2 weeks (ie, 200 mg or 400 mg sparsentan, respectively), then titrate to the target dose after confirmation of tolerability at Week 114. Patients who are taking 1 capsule of study medication (ie, 200 mg sparsentan or 75 mg irbesartan) at the end of the double-blind period will initiate treatment in the open-label extension at 200 mg open-label sparsentan and continue on that dose

throughout the open-label extension. For details regarding dose titration in the open-label extension, see [Section 8.1.2](#); for details regarding dose modifications, see [Section 8.3.2](#).

As in the double-blind period, additional antihypertensive agents are allowed during the open-label extension to maintain blood pressure $\leq 130/80$ mmHg (patients ≥ 18 years of age) or \leq the 75th percentile (patients < 18 years of age; [Banker 2016](#)), with the exception of those that inhibit the RAAS and endothelin systems (see [Section 15.2.1](#) for concomitant medication considerations).

Patients will participate in the open-label extension for up to 156 weeks (see Figure 2), for a total of 268 weeks in the study (ie, double-blind and open-label periods). If the product becomes commercially available during the open-label extension period, eligible patients may transition out of the study and onto commercial product before the end of the open-label extension period. After the patient completes the study (Week 268), if sparsentan is not commercially available, patients may potentially receive sparsentan via alternative means depending upon regulations and commercial status in each country.

Figure 2: Study 021FSGS16010 Overview Flow Chart of the Open-Label Extension

^a See [Section 7.2](#) for eligibility criteria for the open-label extension.

^b The blinded dose the patient is on at Week 108 is dependent on randomization, weight, and ability to tolerate study medication during the double-blind period.

^c Dose for the open-label extension will be based on tolerability as determined at Week 114. Any dose titration for patients who enter the open-label extension with an eGFR value < 30 mL/min/1.73 m² will be at the Investigator's discretion based on the results of the Week 114 assessments. Doses may be modified at any time throughout the open-label extension for safety/tolerability reasons at the Investigator's discretion. In addition, after titration to the target dose, increases above the target doses of 200 mg or 400 mg sparsentan may be considered for patients who, in the Investigator's opinion (and following consultation with the Medical Monitor), would benefit from an increased dose.

^d Patients who enter the open-label extension with an eGFR value < 30 mL/min/1.73 m² and titrate at Week 114 will be contacted by the Investigator at Week 116 to assess tolerance of the higher dose; at the Investigator's discretion, these patients may also come in for an additional visit at this time.

6.3. Patient Completion and Overall Study Completion

6.3.1. Patient Completion of the Double-Blind Period

Each patient will participate in the double-blind period of the study for approximately 6 weeks during the screening phase, followed by 108 weeks of double-blind treatment. At the end of the 108-week treatment period, study medication will be discontinued and replaced with standard-of-care therapy treatment, including treatment with RAAS inhibitors provided there are no contraindications for their use. If the patient was treated with irbesartan at study entry, an alternative ARB at an equivalent dose is required from Week 108 to Week 112. The Investigator may make additional adjustments in antihypertensive medications as necessary to adequately control the patient's blood pressure.

Patients will return to the site for the final (Week 112) visit 4 weeks later. Thus, patients will participate in the double-blind period for a total of approximately 118 weeks or about 30 months.

A patient will be considered as having completed the double-blind period, regardless of whether the patient is on or off study medication, if the patient is followed until Week 112. The need for additional intervention for the treatment of FSGS or the occurrence of safety endpoints do not constitute completion of the double-blind period and are not criteria for withdrawal from the study or study medication.

Patients who successfully complete the final Week 112 Visit will complete the assessments listed in the schedule of events ([Section 15.1](#)). Patients who received blinded study medication throughout the duration of the double-blind period (ie, did not permanently discontinue study medication) may be eligible to enroll in the open-label extension (see [Section 7.2](#)).

6.3.2. Patient Completion of the Open-Label Extension

Eligible patients may participate in the open-label extension for up to 156 weeks. If the product becomes commercially available during the open-label extension period, eligible patients may transition out of the study and onto commercial product before the end of the open-label extension period. After the patient completes the study (Week 268), if sparsentan is not commercially available, patients may potentially receive sparsentan via alternative means depending upon regulations and commercial status in each country.

6.3.3. Overall Study Completion

The study will be considered complete when the last patient completes their final visit.

6.4. Discontinuation of Study Medication

A patient/patient's parents or guardians is/are free to withdraw assent/consent and/or discontinue the patient's participation in the study at any time, without prejudice to subsequent standard-of-care treatment. As part of the informed consent process, only patients who fully understand and agree to full and long-term participation should be consented to participate. In all cases of impending study medication discontinuation, Investigators should discuss options of continuing in the study with the patient (see [Section 6.4.1](#) and [Section 6.4.2](#)). In general, patients should be encouraged to both stay on study medication and remain in the study until study termination.

6.4.1. Temporary Interruption of Study Medication

Patients who temporarily interrupt study medication prior to completion of the study will continue with study visits and assessments according to the Schedule of Study Events ([Section 15.1](#)). Unless contraindicated, treatment should be resumed (titrated at the Investigator's discretion according to [Section 8.3.2](#)) whenever possible (including between visits), and treatment resumption should be considered at every visit following study medication interruption.

6.4.2. Permanent Discontinuation of Study Medication

During the course of this long-term study, it is anticipated that patients may permanently discontinue study medication (sparsentan or irbesartan) for any of the following reasons:

- Receipt of kidney transplant or initiation of RRT
- Any SAE, AE of interest (AEOI; see [Section 10.3](#)), clinically significant laboratory abnormality, intercurrent illness, or other medical condition that indicates to the Investigator that continuation on study medication is not in the best interest of the patient
- Significant protocol deviation (ie, patient failed to meet entry criteria or did not comply with protocol requirements resulting in an unacceptable risk to the patient's health)
- Investigator discretion
- Patient (or parent/legal guardian) decision to stop study medication
- Patient pregnancy
- Diagnosis of Class II-IV CHF
- Hyperkalemia resistant to treatment (see Appendix B, [Section 15.2.2](#) for hyperkalemia management guidelines)
- Termination of the study by the Sponsor, US Food and Drug Administration (FDA), or other regulatory authorities (see [Section 13.4.5](#))
- Lost to follow-up

Therapy to treat relapse (that is a new or substantial change in immunosuppression) during the study is not a reason for permanent study medication discontinuation.

Patients who permanently discontinue study medication during the double-blind period should be encouraged to continue study visits through Week 112 for continued collection of safety and efficacy data despite stopping study medication, but may withdraw consent at any time (see [Section 6.5](#)). Patients who agree to continue regularly scheduled study visits will complete the End of Treatment (EOT) assessments listed in the schedule of events ([Section 15.1](#)) as close as possible to the patient's last dose of study medication. The visit data, including the primary reason for discontinuation of study medication, will be recorded on the EOT electronic case report form (eCRF). Subsequent study visit data will be recorded on the visit-specific eCRF, and the patient's final study visit will be recorded on the End of Study (EOS) eCRF.

For patients who permanently discontinue study medication during the double-blind period, the Investigator should resume standard-of-care treatment, including treatment with appropriate medications, as deemed necessary. If the patient was treated with irbesartan at study entry, an alternative ARB or angiotensin-converting enzyme (ACE) inhibitor must be resumed.

Patients permanently discontinuing study medication who are not willing to continue with regular study visits, but who are willing to continue to provide their information for use in the study will be encouraged to remain in the study. The Investigator will contact the Sponsor's designee to determine the best approach based on the patient's situation.

Patients who permanently discontinue study medication during the open-label extension are encouraged to return to the site for a final visit. No other study visits are necessary. If an EOT visit is completed, study medication cannot be resumed.

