4.1. Summary of Potential Risks

The potential risks for patients treated with sparsentan are a consequence of its dual antagonist properties of both angiotensin and endothelin receptor blockade. Due to its ARB properties, sparsentan imparts a potential risk of acute kidney injury (AKI) due to reductions in intracapillary glomerular pressure, and a risk of hyperkalemia due to lower glomerular filtration rate (GFR) and aldosterone inhibition. In addition, syncope has been identified as a risk due to sparsentan's antihypertensive properties. These risks are accentuated in patients with reduced kidney function, volume depletion, and those being treated with non-steroidal anti-inflammatory drugs (NSAIDs). Studies have also shown that treatment with ERAs is associated with increased rates of edema and congestive heart failure (CHF) in patients with diabetic nephropathy (Mann 2010).

Selective and nonselective endothelin ET_A /endothelin receptor subtype B (ET_B) receptor antagonists are expected to cause fetal harm (harm to a developing embryo) if given to pregnant women. Similarly, ARBs have been shown to reduce fetal renal function and increase fetal and neonatal morbidity and death during the second and third trimesters of pregnancy. However, a recently completed, thorough, scientific evidence-based review of all available toxicology data evaluating the risk of genotoxic and teratogenic effects of sparsentan in male patients and their female partners indicates that, similar to marketed ERAs and ARBs, the requirement for contraception in male study patients is not warranted.

Because of these potential risks, sparsentan should be used with caution in patients with CKD Stages 3 and 4 and with extreme caution in patients with CKD Stage 5 and patients at risk of AKI. Moreover, sparsentan should be avoided in patients with CHF Stages 2 through 4, and in women who are or may become pregnant or who are breastfeeding.

For details regarding all nonclinical and clinical data on sparsentan, as well as warnings, precautions, and contraindications, the Investigator should refer to the appropriate section of the [Investigator's Brochure](#).

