Following a 108-week blinded treatment period, treatment with study medication will be discontinued, and patients may be evaluated for eligibility in the open-label extension using values from the Week 108 visit as screening assessments (see Section 6.2.2). At this time, the Investigator should resume standard-of-care treatment, including treatment with RAAS inhibitors provided there are no contraindications for their use. If the patient was treated with irbesartan at study entry, an alternative ARB at an equivalent dose is required from Week 108 to Week 112. The Investigator may make additional adjustments in antihypertensive medications as necessary to adequately control the patient's blood pressure.

Patients will return to the site for the final visit of the double-blind period 4 weeks after study medication has been discontinued (ie, Week 112; see Figure 1).

Figure 1: Study 021FSGS16010 Overview Flow Chart of the Double-Blind Period

^a Screening may begin after informed consent has been signed. The screening window begins on the day of the patient's first in-clinic study procedure. Patients should be screened within the 6-week screening period; however, under extenuating circumstances the screening period may be extended by a maximum of 2 weeks.

^b For patients who are undergoing washout from RAAS inhibitors.

^c Patients whose body weight is ≤ 50 kg at screening will receive one-half the otherwise specified doses of either sparsentan or irbesartan (active control). Weight will be measured at each visit and the dose increased at the Investigator's discretion if the patient's weight reaches >50 kg.

^d Day 1 events shown will occur in the order in which they are listed.

^e Randomization will be stratified by eGFR value (≥ 30 to <60 mL/min/1.73 m² and ≥ 60 mL/min/1.73 m² for all patients) and UP/C (≤ 3.5 g/g and >3.5 g/g [396 mg/mmol; patients ≥ 18 years of age] or ≤ 2 g/g and >2 g/g [226 mg/mmol; patients <18 years of age]) at screening.

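### Protocol 6.4.2 makes resuming an ARB or ACE inhibitor mandatory after an early stop, without the contraindication exception that accompanies the Week 108 rule

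*Protocol*

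**What the plan says.** Protocol 6.4.2 gives two instructions for patients who permanently stop study medication during the double-blind period. The first is general: the investigator should restart standard of care, "including treatment with appropriate medications, as deemed necessary". The second is specific: "If the patient was treated with irbesartan at study entry, an alternative ARB or angiotensin-converting enzyme (ACE) inhibitor must be resumed".

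The planned stop at Week 108 is handled by a similar pair of sentences in 6.2.1. The first says standard of care should be restarted, "including treatment with RAAS inhibitors provided there are no contraindications for their use". The second says that, for patients on irbesartan at entry, "an alternative ARB at an equivalent dose is required from Week 108 to Week 112".

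The reasons for permanent discontinuation listed in 6.4.2 include "Patient pregnancy" and "Hyperkalemia resistant to treatment". Section 4.1 warns that "ARBs have been shown to reduce fetal renal function and increase fetal and neonatal morbidity and death during the second and third trimesters" of pregnancy. It also attributes to sparsentan's ARB properties "a risk of hyperkalemia due to lower glomerular filtration rate (GFR) and aldosterone inhibition".

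**The concern.** Patients who stop early may have stopped for a safety reason, so a contraindication to RAAS inhibition is a real possibility among them. Yet the early-stop rule is the one that omits the exception. An investigator who follows it to the letter is told to restart one of two drug classes and is given no option to withhold both. For a patient stopped because of pregnancy, one of those classes is the one whose fetal risk the protocol itself describes. What is at stake is the clarity and safety of a single instruction, not the trial's inference.

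**Working it through.** No figure is involved, so the check is a comparison of texts.

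**1. Where the exception appears.**

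| Rule | Location in the protocol | Contraindication exception in the sentence or the one before it |
|---|---|---|
| Week 108 stop | Synopsis, Methodology | Yes |
| Week 108 stop | 6.2.1, main text | Yes |
| Week 108 stop | Figure 1, footnote f | Yes |
| Week 108 stop | 6.3.1 | Yes |
| Week 108 stop | Table 5, footnote j | Yes |
| Early stop | 6.4.2 | No |

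That is 5 of 5 for Week 108 and 0 of 1 for the early stop. In every Week 108 version the exception is in the preceding sentence; the irbesartan sentence itself is unqualified.

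**2. Whether the protocol expects contraindications to occur.** It does. Exclusion criterion 3 for the open-label extension (7.2.2) covers patients who could not start RAAS inhibitors, or developed a contraindication to them, between Weeks 108 and 112. Section 6.4.1, on temporary interruption, also makes an exception for contraindications when it tells sites to restart study medication.

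**3. Which stopping reasons meet the rule.** Section 6.4.2 lists 10 reasons. Two raise the question on the documents' own evidence:

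- *Pregnancy.* Section 10.8 requires study medication to stop at once and foresees that a patient may stay in the study afterwards, so the rule can reach her. Section 4.1 documents fetal harm for the ARB option, in the second and third trimesters. The documents state no fetal harm for ACE inhibitors.
- *Treatment-resistant hyperkalemia.* Section 15.2.2 requires permanent discontinuation if hyperkalemia persists or recurs. Section 8.3.1 explains low starting doses of RAAS inhibitors partly by the risk of harmful potassium rises, and 15.2.1 A counts both ACE inhibitors and ARBs as RAAS inhibitors.

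The count of 2 in 10 is a count of list entries, not of patients or of risk.

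**4. What the rule leaves open.** It states no restart date and no dose. Waiting until a pregnancy is over, or restarting later at a low dose once potassium is controlled, would not breach it. This applies equally to both reasons.

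**5. Reach into the analyses.** SAP 8.5.1.1 and 8.5.1.2 fit the slope models to on-treatment eGFR, and SAP 8.1 ends the on-treatment period 3 days after the last dose. Treatment resumed later than that lies outside these data. The Week 112 secondary analyses (SAP 8.7.2 and 8.7.3) include only patients who completed the 108 weeks of treatment. Their sensitivity analysis at 4 weeks after end of treatment does use values from 14 to 84 days after an early stop (SAP Table 2), so resumed treatment can affect that one.

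**The case against.** The best defence is that 6.4.2 should be read in context, as the Week 108 text must be. There too the irbesartan sentence is mandatory and borrows its exception from the sentence before. In 6.4.2 the preceding sentence leaves treatment to the investigator's judgement, and the same reading would carry that judgement forward. This has some force, but the two lead-in sentences are not equivalent: one names contraindications to RAAS inhibitors, while the other mentions neither. A general permission does not naturally turn a specific obligation that follows it into an option.

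A second defence is that the rule is about substitution. Section 15.2.1 C bars irbesartan for these patients, so the sentence may only be saying which drug to use in its place. That is probably the intent. It is not what the wording says, because the sentence also settles whether a drug is resumed.

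A third is that 13.4 allows departures from the protocol to protect patients, and 13.3 exempts changes that remove an immediate hazard. Both stand and lower the practical risk. Neither corrects the instruction.

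It is also fair to say that an unscheduled stop differs from a planned one, so identical wording is not required. That explains the freedom on drug class, dose and timing. It does not explain the missing exception.

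A reader might go further and infer that the protocol obliges a pregnant patient to take a drug it calls harmful. The documents do not support that. No restart date is set, the ACE inhibitor option carries no stated fetal harm in these documents, and the ARB warning is confined to the second and third trimesters.

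**Conclusion.** The omission is real and the severity is minor. The literal rule gives no option not to resume for patients who may have a contraindication, and two of the section's own stopping reasons make such patients foreseeable. The freedom on timing and dose, together with the safety exception in 13.4, limits the practical risk for both reasons.

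The rule concerns only patients on irbesartan at entry who stop early in the double-blind period. The documents do not say how many there are. Nor do they say whether anyone was still in that period at Amendment 9, dated 18 January 2024; if nobody was, the point has no practical consequence.

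The conclusion that the primary analyses are unaffected rests on the on-treatment restriction in the SAP. It would be wrong to infer from this point any bias in the primary slope comparison. It would also be wrong to infer a defect in the Week 108 text, where the exception is already in place.

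**What to change.** In 6.4.2, keep the sentence "If the patient was treated with irbesartan at study entry, an alternative ARB or angiotensin-converting enzyme (ACE) inhibitor must be resumed" and add at its end the proviso that closes "including treatment with RAAS inhibitors provided there are no contraindications for their use", so that an alternative ARB or ACE inhibitor is required only where neither is ruled out by a contraindication. The Week 108 text needs no change.

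Section 13.3 requires protocol changes to be documented by amendment, with ethics committee approval and regulatory approval where required. A site letter may alert investigators in the meantime but cannot replace the amendment. The change is worth making only if patients remain in the double-blind period.

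The drafting cost is one clause, plus the usual amendment process. Visits, data collection, sample size and planned analyses stay as they are. The sensitivity analysis at 4 weeks after end of treatment would be touched only through patients who have a contraindication.

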6.5. Discontinuation of the Patient from the Study

Patients are free to withdraw consent and/or discontinue participation in the study at any time without prejudice to subsequent standard-of-care treatment. A patient's participation in the study may also be discontinued at any time at the discretion of the Investigator or Sponsor. Patients may also be discontinued from the study if the study is terminated (see [Section 13.4.5](#)).

Patients may be permanently discontinued from the study for any of the following reasons:

- Death
- Voluntary withdrawal of patient/guardian assent/consent (complete withdrawal of consent requires a patient's/parent's/guardian's refusal of ALL methods of follow-up noted in the informed consent form [ICF])
- Termination of the study by the Sponsor, US FDA, or other regulatory authorities (see [Section 13.4.5](#))
- Lost to follow-up

In general, patients should be encouraged to remain in the study until they complete the double-blind period. A patient who permanently discontinues from the study during the double-blind period will complete the early termination (ET) assessments listed in the schedule of events ([Section 15.1](#)) as close as possible to the patient's last dose of study medication. The visit data, including the primary reason for premature discontinuation from the study, will be recorded on the EOS eCRF.

